# **List of Abbreviations**

Abbreviation or Specialized Term	Definition
ABPM	Ambulatory blood pressure monitoring
AE	Adverse event
AUC	Area under the concentration-time curve
CGM	Continuous glucose monitoring
C max	Maximum observed concentration
ECG	Electrocardiogram
FFA	Free fatty acids
FPG	Fasting plasma glucose
GLP-1	Glucagon-like peptide-1
HbA1c	Hemoglobin A1c
ITT	Intent-to-Treat
IXRS	Interactive voice/web response system
LOCF	Last observation carried forward
MAGE	Mean amplitude of glucose excursion
MMTT	Mixed-meal tolerance test
PD	Pharmacodynamics
PK	Pharmacokinetics
SPP	Statistical Programming Plan
SC	Subcutaneous
SD	Standard deviation
T2DM	Type 2 diabetes mellitus

Abbreviation or Specialized Term	Definition
t max	Time to maximum-observed concentration
ULN	Upper limit of normal range

#### 1 INTRODUCTION

This document describes the statistical analysis methodology for protocol D5670C00007, a Phase 2a exploratory randomized, double-blind, placebo-controlled study to evaluate the efficacy and safety of MEDI0382 versus placebo in overweight/obese subjects with type 2 diabetes mellitus (T2DM) treated with dapagliflozin and metformin. This document details the statistical summaries relating to each study objective and describes the general conventions and definitions that will be used. In addition, a set of table templates and specifications will be included in a statistical programming plan (SPP) to complement this document.

#### 2 STUDY OVERVIEW

### 2.1 Study Objectives

### 2.1.1 Primary Study Objective(s)

To compare the change in glucose area under the concentration-time curve (AUC) as measured by a standardized mixed meal tolerance test (MMTT) in subjects treated with dapagliflozin and metformin receiving MEDI0382 or placebo for 28 days

### 2.1.2 Secondary Study Objectives

- To compare the safety and tolerability profile of MEDI0382 (titrated up to a dose level of 300 µg subcutaneous [SC]) compared to placebo after 28 days of treatment in subjects treated with dapagliflozin and metformin
- To evaluate the pharmacokinetics (PK) profile of MEDI0382 and dapagliflozin (in subjects treated with dapagliflozin, metformin, and MEDI0382) and dapagliflozin (in subjects treated with dapagliflozin, metformin, and placebo)
- To evaluate 24-hour glucose control as measured by continuous glucose monitoring (CGM) in subjects treated with dapagliflozin and metformin receiving MEDI0382 or placebo for 28 days

## 2.1.3 Exploratory Study Objectives

• To compare additional measures of glucose control (fasting plasma glucose [FPG] and hemoglobin A1c [HbA1c]) in subjects treated with dapagliflozin and metformin receiving MEDI0382 or placebo for 28 days

[figure not shown]
- To evaluate pancreatic and incretin hormone AUC profiles (ie, active glucagon-like peptide-1 [GLP-1], glucagon, insulin, and c-peptide) as measured by MMTT in subjects treated with dapagliflozin and metformin receiving MEDI0382 or placebo for 28 days
- To compare the fasting free fatty acid (FFA) levels in subjects treated with dapagliflozin and metformin receiving MEDI0382 or placebo for 28 days
- To compare plasma ketone profile (β-hydroxybutyrate) in subjects treated with dapagliflozin and metformin receiving MEDI0382 or placebo for 28 days
- To compare the change in body weight after 28 days of treatment with MEDI0382 or placebo in subjects treated with dapagliflozin and metformin
- To evaluate 24-hour urinary glucose excretion in subjects treated with dapagliflozin and metformin receiving MEDI0382 or placebo

### 2.2 Study Design

This is an exploratory randomized, double-blind, placebo-controlled study to evaluate the efficacy and safety of MEDI0382 versus placebo in overweight/obese subjects with T2DM treated with dapagliflozin and metformin dual therapy. Subjects will participate in the study for up to 20 weeks, including a screening period of up to 60 days, a 4-week run-in period (for subjects on metformin monotherapy only), a 4-week treatment period, and a 4-week post-treatment follow-up period.

The study will enroll subjects with T2DM treated either with metformin monotherapy or with metformin and dapagliflozin dual therapy. After the screening period of up to 60 days, subjects previously treated with metformin monotherapy only will enter an open-label, run-in period where subjects will be administered oral dapagliflozin 10 mg a day for 4 weeks. Enrolled subjects who are already treated with metformin and dapagliflozin dual therapy will continue this dual therapy throughout the study and can be randomized after the screening period without entering the run-in period. All subjects (ie, on monotherapy and dual therapy) entering the double-blind treatment period will receive dapagliflozin 10 mg a day. (Figure 2.2-1)

Figure 2.2-1 Study Flow Diagram

BMI = body mass index; HbA1c = hemoglobin A1c; MTD = maximum-tolerated dose; N = number of subjects; QD = once daily; SC = subcutaneous; T2DM = type 2 diabetes mellitus.

- \* Run-in period only for subjects on metformin monotherapy only at screening
- \*\* Subject on metformin and dapagliflozin dual therapy at screening move directly from screening to double blind treatment period

### 2.3 Treatment Assignment and Blinding

An Interactive voice/web response system (IXRS) will be used for assignment of dapagliflozin tablet bottles (where required), randomization to a treatment group, and assignment of blinded MEDI0382 or placebo investigational product kit numbers. A subject is considered randomized into the study when the investigator notifies the IXRS that the subject meets eligibility criteria, and the IXRX provides the assignment of investigational product kit number to the subject.

Eligible subjects will be randomized at a 1:1 ratio following screening to receive either MEDI0382 SC or placebo SC. The IXRS will assign a unique randomization code and treatment group to the subject at each randomization. Subjects who withdraw from the study may be replaced, if deemed necessary by the medical monitor, to ensure that safety data are collected on a sufficient number of subjects.

This is a double-blind study in which MEDI0382 and placebo are not identical in the prefilled syringe titration volumes. Neither the subject nor any of the investigator or sponsor staff who are involved in the treatment or clinical evaluation of the subjects will be aware of the treatment received (ICH E9).

The different fill volumes of investigational product (MEDI0382 and placebo) and the relative position of the plunger rods will be visually distinct during administration. To maintain the blind, investigational product (MEDI0382 and placebo) prefilled syringes will be handled by an unblinded investigational product manager or unblinded study personnel that will not be involved in the treatment or clinical evaluation of subjects. An unblinded qualified designee may administer investigational product to subjects during in-clinic visits.

An independent investigational product monitor will also be unblinded to perform investigational product accountability. In the event that a treatment allocation for a subject becomes known to the investigator or other study staff involved in the management of study subjects, the sponsor must be notified immediately. If the treatment allocation for a subject needs to be known to treat an individual subject for an adverse event (AE), the investigator must notify the sponsor immediately. The site will maintain a written plan detailing which staff members are blinded/unblinded and the process of investigational product administration used to maintain the blind.

### 2.4 Sample Size

A total of 46 subjects are planned for the study. Each of the 2 treatment groups will be randomized at a 1:1 ratio to receive (a) MEDI0382 with dapagliflozin and metformin administered simultaneously or (b) placebo with dapagliflozin and metformin administered simultaneously. A sample size of 23 subjects in each treatment group will provide a study power > 95% to detect a difference of 30% between treatment groups in relative change from baseline in glucose AUC0-4h at a two-sided alpha of 5%, assuming a common standard deviation (SD) of 20%. This sample size will also provide a study power > 95% to detect a difference of 225 hr•mg/dL between treatment groups in absolute change from baseline in glucose AUC0-4h at a two-sided alpha of 5%, assuming a common SD of 150 hr•mg/dL. The SD assumptions are based the result of 300 μg cohorts in a prior study (D5670C00002).

#### 3 STATISTICAL METHODS

#### 3.1 General Considerations

Data will be presented in data listings sorted by treatment group, subject number, and date collected, where appropriate. Tabular summaries will be presented. Categorical data will be summarized by the number and percentage of subjects within each category. In general, continuous variables will be summarized by descriptive statistics including mean, standard deviation, median, minimum, and maximum. For some variables, the geometric mean and 95% CI will be presented.

All available data will be included in the analyses and missing data will not be imputed, except in a last observation carried forward (LOCF) analysis and as specified in the

calculation of the AUC values. When LOCF is used to impute for missing post-baseline data, only post-baseline data will be carried forward (eg, baseline data will not be carried forward). Unless otherwise specified, baseline values will be defined as the last valid assessment prior to the first administration of study medication (MEDI0382 or placebo).

All statistical tests will be 2-sided at an alpha level of 5% unless stated otherwise. There will be no adjustment for multiplicity.

Data analyses will be performed using SAS® version 9.3 or higher (SAS Institute Inc., Cary, NC). The analytical results generated from SAS programs will follow MedImmune SAS programming standards and will be validated according to MedImmune SAS validation procedures.

#### 3.2 Analysis Populations

The analysis populations are defined in Table 3.2-1.

Table 3.2-1 Analysis Populations

Population	Description
Intent-to-treat (ITT)	Randomized subjects who receive any investigational product
Population	(MEDI0382 or placebo) analyzed according to their randomized treatment group.
As-treated	Subjects who receive any investigation product (MEDI0382 or
Population	placebo) analyzed according to the treatment they actually receive.
MEDI0382 PK	Subjects who receive at least 1 dose of investigational product
Population	(MEDI0382 or placebo) and have at least 1 MEDI0382 PK sample
	taken that is above the lower limit of quantitation.
Dapagliflozin PK	Subjects who receive at least 1 dose of investigational product
Population	(dapagliflozin or placebo) and have at least 1 dapagliflozin PK sample
	for dapagliflozin taken that is above the lower limit of quantitation.
Ketone PK	Subjects who receive at least 1 dose of investigational product
Population	(MEDI0382 or dapagliflozin or placebo) and have at least 1 ketone PK
	sample taken that is above the lower limit of quantitation.

### 3.3 Study Subjects

#### 3.3.1 Subject Disposition and Completion Status

A summary of subject eligibility and randomization as well as treatment group received (including a summary of subjects randomized but not treated) will be provided. In addition, disposition of subjects throughout the study with respect to completion of treatment and end of study will be provided.

#### 3.3.2 Demographics and Baseline Characteristics

Demographic information related to sex, age, race, weight, height, and body mass index (BMI) will be presented by treatment group and for all subjects combined. A summary of baseline disease characteristics may include, but not be limited to duration of T2DM, diabetes complications, HbA1c, fasting plasma glucose, eGFR, background therapy for diabetes (eg, metformin monotherapy or metformin + dapagliflozin).

#### 3.3.3 Study Drug Exposure

The duration of exposure (number of days dosed) of MEDI0382 and dapagliflozin will be summarized by treatment group with descriptive statistics and by frequency.

#### 3.3.4 Concomitant Medications

Concomitant medications will be coded using current World Health Organization Drug Dictionary. The number and percentage of subjects who took concomitant medications will be summarized by the highest anatomical therapeutic chemical class and preferred term by treatment group for the As-treated Population. The summary of concomitant medications will include all concomitant medications taken on or after the date of first dose of study medication or any concomitant medication started prior to first dose study medication that continued beyond the date of first dose of study medication.

# 3.4 Efficacy Analyses

### 3.4.1 Primary Efficacy Endpoint(s) and Analyses

#### 3.4.1.1 Primary Efficacy Endpoint(s)

- Change from baseline (Day -1) to the end of 28 days of treatment (Day 28) in glucose AUC from 0 to 4 hours (AUC0-4h) as measured by a MMTT
- Percentage change from baseline (Day -1) to the end of 28 days of treatment (Day 28) in glucose AUC0-4h as measured by a MMTT

#### 3.4.1.2 Handling of Dropouts and Missing Data

No missing data imputation will be used for the primary efficacy analysis since there is only one post-baseline data collected for the primary efficacy endpoint. If any glucose values used in the calculation of the glucose AUC are missing, the AUC will be calculated as described in the SPP.

#### 3.4.1.3 Primary Efficacy Analysis

The primary efficacy analysis will be based on the ITT population. The primary endpoints, change and % change from baseline to the end of 28 days of treatment in glucose AUC0-4h as measured by a MMTT, will be summarized by treatment group. Statistical comparisons of these endpoints between MEDI0382 and placebo treatment groups will be performed using an analysis of covariance by adjusting baseline value and treatment group.

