1 INTRODUCTION

1.1 Disease Background

The rising prevalence of type 2 diabetes mellitus (T2DM) and obesity is a cause of substantial health and economic burden worldwide. In many cases of T2DM, significant weight loss (typically 5% of body weight or more) can promote improvements in glycemic control, and it may even slow or reverse disease progression ([Petersen et al, 2005](#)). Many existing therapies for T2DM focus upon lowering blood glucose; however, there is a major unmet need for treatments that improve glycemic control and achieve disease-modifying weight loss simultaneously.

Achieving optimal glycemic control early in the course of T2DM is an important goal for patients and treating physicians. Early interventions may prevent disease progression and decrease the risk of developing long-term T2DM comorbidities. Traditional step-wise pharmacotherapy begins with metformin as first-line therapy for the treatment of T2DM; however, patients often require combination therapy to achieve and maintain glycemic control because of the progressive nature of the disease. The combination of dapagliflozin and metformin is a common dual oral therapy in T2DM patients who fail treatment with monotherapy. The addition of a third noninsulin agent may be considered in patients with hemoglobin A1c (HbA1c) above the individualized target after 3 months of treatment with a combination of 2 drugs.

Dapagliflozin (Forxiga) is a potent and highly selective inhibitor of sodium-glucose cotransporter-2 (SGLT2) and is currently approved for improvement of glycemic control in adults with T2DM as monotherapy or as add-on combination therapy with metformin and other oral antiglycemic therapies. SGLT2 is localized to the renal proximal tubule where it reabsorbs most of the approximately 180 g of glucose normally filtered through the glomeruli each day. Inhibition of glucose reabsorption leads to glycosuria and consequently to glycemic-lowering effects including decreased levels of fasting plasma glucose (FPG) and HbA1c. In addition, the caloric loss associated with the excreted glucose is associated with body weight loss. Dapagliflozin has a half-life of approximately 12 hours, thus allowing for once daily oral administration. Additional information can be found in Forxiga's Summary of Product Characteristics ([Forxiga Summary of Product Characteristics, 2017](#)).

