3 STUDY DESIGN

3.1 Description of the Study

3.1.1 Overview

This is an exploratory randomized, double-blind, placebo-controlled study to evaluate the efficacy and safety of MEDI0382 versus placebo in overweight/obese subjects with T2DM treated with dapagliflozin and metformin dual therapy.

The study will enroll subjects with T2DM treated either with metformin monotherapy or with metformin and dapagliflozin dual therapy. After the screening period of up to 60 days, subjects treated with metformin monotherapy only will enter a 4-week run-in period where subjects will be administered oral dapagliflozin 10 mg a day, which will be provided by the sponsor. Enrolled subjects that are already treated with metformin and dapagliflozin dual therapy will continue this dual therapy throughout the study and can be randomized after the screening period without entering the run-in period. All subjects (ie, on monotherapy and dual therapy) entering the double-blind treatment period will receive dapagliflozin 10 mg a day, which will be provided by the sponsor.

Forty-six subjects are expected to participate in the study for up to 20 weeks including a screening period of up to 60 days, a 4-week run-in period (for subjects on metformin

monotherapy only), a 4-week treatment period, and a 4-week follow-up posttreatment period. There will be a total of 2 inpatient stays with a duration of 2 to 3 days.

Four-week run-in period

After screening, subjects on metformin monotherapy only will begin an open-label, run-in period on Day -28 and will receive oral dapagliflozin 10 mg a day for 28 days prior to randomization. On Day -14, subjects will return to the clinical unit for an abbreviated physical examination, vital signs, and blood collection for safety laboratory assessments.

Subjects on dual therapy (metformin plus dapagliflozin) can be randomized after the screening period. In addition, all subjects will be given diet and lifestyle advice to follow for the duration of the study.

Four-week treatment period

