4.6 Treatment Assignment and Blinding

4.6.1 Methods for Assigning Treatment Groups

An IXRS will be used for assignment of dapagliflozin tablet bottles (where required), randomization to a treatment group and assignment of blinded MEDI0382 or placebo investigational product kit numbers. A subject is considered randomized into the study when the investigator notifies the IXRS that the subject meets eligibility criteria, and the IXRS provides the assignment of investigational product kit number to the subject.

Eligible subjects will be randomized at a 1:1 ratio following screening to receive either MEDI0382 SC or placebo SC. The IXRS will assign a unique randomization code and treatment group to the subject at each randomization. Subjects who withdraw from the study may be replaced, if deemed necessary by the medical monitor, to ensure that safety data are collected on a sufficient number of subjects.

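### Background therapy is neither a named stratification factor nor a term in the HbA1c, body weight and ambulatory blood pressure ANCOVAs, which costs some precision if new and established dapagliflozin users still drift differently after baseline

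*SAP*

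**What the plan says.** Protocol 3.1.1 enrols two groups. In one, "subjects treated with metformin monotherapy only will enter a 4-week run-in period" on dapagliflozin 10 mg, which lasts 28 days before randomization. The other group is already on metformin plus dapagliflozin and skips the run-in; Protocol 4.1.2 (criterion 5) requires at least 3 months of stable dual therapy before screening.

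On allocation, Protocol 4.6.1 says: "Eligible subjects will be randomized at a 1:1 ratio following screening". SAP 2.3 repeats this. Neither document names a stratification factor.

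On the model, SAP 3.4.1.3 says that the primary comparison is "performed using an analysis of covariance by adjusting baseline value and treatment group". SAP 3.4.3.2 carries this to HbA1c and body weight, with last observation carried forward. SAP 3.6.5.1 specifies treatment and baseline value for ABPM. The baselines are Day -2 for HbA1c and ABPM, and Day 1 for weight.

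SAP 3.3.2 lists "background therapy for diabetes (eg, metformin monotherapy or metformin + dapagliflozin" among the baseline characteristics that a summary may contain. No adjusted, subgroup or sensitivity analysis uses it.

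**The concern.** Run-in subjects reach baseline after about four weeks of dapagliflozin; dual-therapy subjects reach it after more than three months. The protocol gives reasons to expect an effect of dapagliflozin on the outcomes concerned. Section 1.1 says that it lowers fasting glucose and HbA1c, and that "the caloric loss associated with the excreted glucose is associated with body weight loss". Section 1.6.3 links it to a modest fall in blood pressure. If part of that effect is still developing at baseline in run-in subjects, their HbA1c, weight or ABPM would keep falling during the treatment period for a reason unrelated to MEDI0382. The baseline value of the endpoint records where a subject starts, not the slope that follows.

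Two consequences would follow. The difference between the groups goes into the residual variance. And if the arms happen to differ in their run-in share, part of the estimated treatment difference reflects that share, and the planned model has no term to separate the two.

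**Working it through.** **Inputs from the documents.** "A sample size of 23 subjects in each treatment group" (SAP 2.4), so 46 in total. The design claims "power > 95% to detect a difference of 30% between treatment groups" in relative change, "at a two-sided alpha of 5%, assuming a common standard deviation (SD) of 20" per cent. For absolute change, the figures are 225 hr•mg/dL with SD 150. Both give a standardized difference of 1.5.

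**Assumed inputs.** The documents give neither the mix of the two groups nor any difference in drift. I take p, the share of one group, as 10% to 50%, and g, the difference in mean change between the groups, as 0.25 to 1.0 within-group SD.

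**1. The plan's own power.** The standard error of a difference, in SD units, is √(2/23) = 0.295. Power = Φ(1.5/0.2949 − 1.96) = Φ(3.127) = 99.9% for both primary endpoints. The noncentral t on 44 df also gives 99.9%. The stated power is confirmed; 12 per arm would already give 95%.

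**2. Residual SD when the factor is left out.** Inflation = √(1 + g²p(1 − p)).
- p = 10%, g = 0.25: √1.0056 = 1.003, or 0.3%.
- p = 50%, g = 0.5: √1.0625 = 1.031, or 3.1%.
- p = 50%, g = 1.0: √1.25 = 1.118, or 12%.

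Squaring these gives the equivalent number of extra subjects for the same precision: 0.6% at the low end and 25% at the high end.

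**3. Chance imbalance without stratification.** With K subjects of one group among 46, the number falling in one arm of 23 is hypergeometric. If that number is x, the difference in share between the arms is |2x − K|/23.

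| K | Share | SD of the difference | Chance of ≥ 20 points |
|---|---|---|---|
| 5 | about 10% | 9 points | 4.9% |
| 9 | about 20% | 12 points | 13.5% |
| 14 | about 30% | 14 points | 10.8% |
| 23 | 50% | 15 points | 23.8% |

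The last column is unstable. With odd K, a difference of 5 subjects (5/23 = 21.7 points) crosses the threshold; with even K it takes 6 (26.1 points). So K = 22 or 24 gives 13.9% instead of 23.8%, and K = 13 gives 18.9% instead of the 10.8% at K = 14. The SD column is the steadier summary.

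**4. Shift at a 20-point imbalance.** Shift = 0.20 × g, which is 0.05 SD at g = 0.25 and 0.20 SD at g = 1.0. Against the standard error of 0.295 SD, the largest is 0.20/0.295 = 0.68 of a standard error.

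**5. Steps 2 and 3 describe one effect.** At p = 50% and g = 1.0, adding the variance due to imbalance to the sampling variance gives 0.295² + 0.149² = 0.0870 + 0.0222 = 0.1092, with square root 0.330. Inflating the standard error by step 2 gives 0.295 × 1.118 = 0.330. The planned model's standard error already covers the chance shift on average.

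**6. Primary endpoint, worst case.** Taking 20% as the within-group SD with p = 50% and g = 1.0: Φ(5.087/1.118 − 1.96) = Φ(2.59) = 99.5%.

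**The case against.** The strongest case against acting has five parts.

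- **The study is exploratory.** It is a Phase 2a trial without multiplicity control. HbA1c and weight are exploratory endpoints, and ABPM is a safety measure. This stands, and it limits the importance of the point.
- **Chance imbalance is not bias.** A reader might infer that the plan biases the MEDI0382 effect. It does not. Allocation is randomized, so the estimate is unbiased over repeated randomizations, and step 5 shows that the standard error already reflects the extra variation. What remains is lost precision, plus a shift in the particular trial if the arms turn out unequal.
- **The primary endpoint is safe.** A reader might infer a threat to it, because the model is set out there. Step 6 shows essentially none.
- **The drift is not documented.** Protocol 1.1 and 1.6.3 say what dapagliflozin does, not that its effect is still developing after 28 days. The case is weakest for blood pressure, where the documents give no time course. This stands; with zero drift difference, the extra term gains nothing.
- **The design already helps.** The run-in puts everyone on dapagliflozin 10 mg before baseline, and baseline is in the model. This reduces the problem but does not remove change that continues after baseline.

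Nor does the two-term model govern every endpoint. Weight loss of at least 5% uses logistic regression (SAP 3.4.3.2), β-hydroxybutyrate parameters and urinary glucose are descriptive only (SAP 3.5.1.2), and so are clinic vital signs.

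**Conclusion.** The point holds as an inexpensive gain in precision and interpretability for HbA1c, body weight and ABPM. Two groups with different dapagliflozin histories are pooled, and a factor known at screening is used in neither the allocation nor the models. The size rests wholly on assumed shares and drift differences: at the low end the loss is negligible, and at the high end it equals the loss of a fifth of the sample (1 − 1/1.25). The documents do not support a claim of systematic bias, of weak primary power, or of established drift after day 28. The practical argument for acting is that adjustment prespecified before unblinding is more credible than adjustment chosen after an imbalance is seen.

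**What to change.** Before unblinding, add background therapy at screening (metformin alone with run-in versus metformin plus dapagliflozin) as a fixed factor in the ANCOVAs of SAP 3.4, 3.5 and 3.6.5.1. Define it so that subjects washed out of another oral agent (Protocol 4.1.2, criterion 6) are classified without ambiguity. State also whether the logistic model for weight loss is to carry the factor.

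In SAP 3.3.2, make the by-arm summary of background therapy mandatory. Make the factor a stratification factor in the IXRS only if randomization has not started.

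The cost is one model term and one residual degree of freedom (46 − 3 = 43 becomes 46 − 4 = 42). The protocol already needs the variable to decide who enters the run-in. There is no gain if the two groups do not drift differently.
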